A published pilot study of hypnotherapy for IBS delivered entirely through audio recordings by co-investigator [name] and his colleagues serves as a model for the hypnosis treatment in this FD trial¹⁹. That study found that IBS patients who completed a seven-session self-administered audio home hypnosis treatment course were twice as likely (53% vs 26%) to have a reduction in their gastrointestinal symptoms by half or more at 6 months compared to matched control patients of the same age and sex and equal symptom severity who only received standard medical care. We will script the audio-recorded hypnosis protocol in the present trial to be similar in structure and therapy approach, as IBS and functional dyspepsia are both functional GI disorders and have many similarities and a high degree of overlap (the intervention tested in the prior hypnosis trial by Calvert et al., that showed high success in FD treatment, also utilized modified IBS hypnosis treatment for that purpose).

III. Study Aims

The purpose of this pilot study is to develop and test a hypnotherapy (HYP) treatment program for functional dyspepsia (FD) that can be self-administered using on-line audio recordings. We hypothesize that patients will be receptive to the self-administered treatment design and willing to participate and complete the 12-week treatment program.

Furthermore, we expect that patients will experience a significant reduction in FD symptoms following the intervention. Our specific aims include:

Aim 1: Feasibility and Acceptability of Treatment

The study will assess whether patients with FD will be willing to participate in the on-line treatment program and the majority of patients enrolled in the study will complete the 12 week program, utilize the materials sufficiently, and report average to above average satisfaction with treatment.

Aim 2: Treatment Effectiveness

The primary endpoint for Aim 2 is significant reduction in pre- to post- treatment FD symptom scores. Secondary endpoints include significant improvements in pre- to post-treatment score on psychological indices (e.g., anxiety) and disease-specific quality of life.

IV. Administrative Organization

All administrative activities related to the study will take place within the Division of Gastroenterology and Nutrition at Loyola University Medical Center (LUMC).

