Administrative offices for the division are located in the Fahey Building on the LUMC campus where office furniture, file cabinets, and use of essential equipment (e.g., copier, fax, phone, computer) will be provided.

V. Study Design

a. Experimental design of the study:

This is a non-randomized observational study designed to provide preliminary data on the feasibility and effectiveness of a self-administered HYP treatment for FD.

b. Study population general description

Eligible patients will be referred by Gastroenterologists within the Digestive Health Program at Loyola University Medical Center and will have received a diagnosis of functional dyspepsia. Additionally, any patients with functional dyspepsia referred by outside providers to [name] GI Behavioral Medicine Service at LUMC will be made aware of the study.

c. Sample size determination and power analyses

We will enroll 23 adults with FD from the Loyola University Medical Center outpatient gastroenterology practices, with the aim of assessing feasibility and acceptability of HYP treatment using on-line audio recordings. Sample size was determined for aim 1 of the study. Allowing for up to 20% drop-out and having at least 16 patients complete the study through the end of treatment (where the primary endpoint will be measured) will provide sufficient participant feedback on the web interface as well as the pilot data needed to power a future randomized controlled trial.

d. Study outcomes/endpoints

The primary endpoint for this study will be FD symptom scores. Secondary endpoints will be disease-specific quality of life, psychological indices, and patient satisfaction.

VI. Study Procedures

a. Subject selection procedures:

We will enroll 23 adults with FD.

Inclusion criteria

- (1) Diagnosis of functional dyspepsia by a gastroenterologist
- (2) Meeting ROME IV diagnostic criteria for functional dyspepsia
- (3) At least 18 yrs of age (no upper age limit)
- (4) Able to give informed consent
- (5) English speaking
- (6) Have daily personal access to the Internet via laptop or desktop computer, tablet or a smartphone.

Exclusion criteria

- (1) Concomitant organic gastrointestinal disease
- (2) Diagnosed or presenting with serious mental illness (e.g., eating disorder, schizophrenia, psychosis, obsessive-compulsive disorder, post-traumatic stress disorder, or a dissociative disorder)

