4. What happens with screen failures (including any data gathered during screening)? Data will not be collected on patients that are screened as ineligible for the study. However, these patients will be provided with recommendations for alternative treatment options by their gastroenterologist (medications, diet changes), alternative psychological treatments within the Loyola GI behavioral medicine program, or a referral to an outside provider depending on patients' needs.

- b. Randomization procedures (if applicable): N/A
- c. Study Intervention

Patients will be given access to a password protected website containing HYP treatment materials. They will be instructed by the study coordinator to log on to the website within 1 week to complete baseline assessment questionnaires and watch an instructional video. This video will be pre-recorded by [name] (study PI). The content of the video will include educational information about the patient's diagnosis, provide rationale for hypnotherapy treatment, set expectations for treatment, and dispel myths about hypnotherapy. The video will also provide instructions on implementing the treatment protocol, including guidance on selecting a time and place to practice hypnotherapy and recommendations for weekly practice with audio recordings (5x per week). See Appendix B for a full script of this introductory video (video will be filmed after we receive IRB approval).

We have developed a 7- session, hypnosis protocol for functional dyspepsia that is similar to an evidence-based protocol for irritable bowel syndrome developed by co-investigator [name], which has been found to be efficacious in 7 published studies²⁴. This protocol was jointly scripted by Drs. [name] and [name], and is based on the successful scripted therapy approach for IBS, with appropriate adaptations. See Appendix C for the full scripted protocol of the 7 hypnotherapy sessions as well as the shorter practice session that will be audio recorded. This will be the full content of the audio recordings, subject to final minor edits and polishing, prior to recording which will be scheduled after we receive IRB approval.

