In a separate study management web page, study staff will be able to log in to see which main hypnosis sessions each patient has completed and whether they are significantly overdue for completing the next session, and also whether they have completed the study questionnaire at the expected time points, and the frequency of practice of the shorter exercises for each individual. This information will alert the study staff to contact patients who are not keeping up with study tasks with reminders.

d. Study Assessments and Activities

Study Assessments:

At baseline (week 0), week 6 (mid-treatment), week 12 (post-treatment), and at 12 weeks following end of treatment (i.e., 3 month follow up) participants will be asked to complete a set of questionnaires listed below. See Appendix D for a complete list of survey items and questionnaires. Study assessments will be administered electronically through the password-protected online platform via highly secure Qualtrics Research Suite Software, and all questionnaire data will be collected in a fully de-identified manner that neither obtains nor stores online any information that can reveal the personal identify of participants. Participants will be assigned a unique subject code that will be associated with his/her questionnaire data.

Patients will be paid for completing each of the assessments: They will receive Amazon gift certificates in the amount of \$25 each time, except the amount will be \$50 at the end-of-treatment point (as this is the most important assessment time point). Thus, patients will receive a total compensation of \$125 for completing all 4 assessments in the study.

Additionally, participants will be invited to participate in a phone interview to provide qualitative feedback about their experience with the intervention and using the web interface. This will be a semi-structured

interview with the research coordinator to assess patient experience and satisfaction. The interview will take place within one month following the final hypnotherapy session.

Patients will complete the following questionnaires:

- **Demographics** and psychosocial history (administered at week 0 only): basic demographic data (e.g., age, gender, education) as well as disease related information (symptom severity, medication use).

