- **The Rome IV Dyspepsia Module** will be administered at baseline to confirm diagnosis of functional dyspepsia. This self-report questionnaire is used to diagnosis functional GI disorders based on Rome IV criteria.²
- **The Patient Assessment of Upper Gastrointestinal Symptom Severity Index (PAGI-SYM)** will be administered to assess symptom severity. The PAGI-SYM measures 20 dyspeptic symptoms on a 6-point Likert scale, 0 (no complaints) – 5 (severe complaints), subdivided into six subscales: heartburn/regurgitation, nausea/vomiting, postprandial fullness/early satiety, bloating, upper abdominal pain, and lower abdominal pain. The measure has demonstrated good reliability and validity for measuring symptom severity in patients with functional dyspepsia.²⁵
- **The Short Form Napean Dyspepsia Index (NDI-SF)** is a 10-item disease specific quality of life questionnaire developed for clinical trials in functional dyspepsia. The NDI has been established to have excellent psychometric properties²⁶ and responsiveness to treatment change has been confirmed²⁷ and the 10-item short form is recommended for use in clinical trials.²⁸
- **Visceral Anxiety (VSI):** The VSI is a 15-item questionnaire that will be used to assess gastrointestinal specific anxiety²⁹. This measure assesses fears of GI symptoms and is a predictor of symptom severity in patients with functional GI disorders. The VSI uses a 6 point likert scale response format with total scores ranging from 0 to 75; higher scores indicate more severe symptom-related anxiety.
- **The Brief Symptom Inventory (BSI)** will be used to assess depression, anxiety, and somatization.³⁰ The BSI is an 18-item questionnaire using a 5-point likert scale with scores ranging from 0 to 68; higher scores indicate higher levels of distress.
- **Thought Impact Scale- Short Form (TIS-SF).** This 17-item questionnaire is a short-form version of the Thought Impact Scale, a newly validated measure designed to predict clinical response to hypnosis treatment. The TIS-SF will be administered at baseline only to assess whether the traits that it measures (i.e., subconscious

connectedness) correlates with the degree of FD symptom improvement in the study.³¹

- **Adherence to Hypnosis Practice:** Use of hypnosis sessions will be recorded automatically by the audio player page on the treatment web page, to track frequency of home practice of hypnotherapy by the HYP intervention participants.

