Aim 2: Treatment Effectiveness. Methods: The primary analyses to estimate treatment effects in this study will be linear mixed effects regression analysis. Mixed effects regression is flexible for modeling linear and nonlinear trends over time and robust to data missing at random. A separate mixed effects model will be specified for each of our primary outcome variables (DSSI and NDI-SF). Residual analysis will be performed and transformations of outcome measures will be applied as necessary. These models will estimate treatment effects at each follow-up time point controlling for baseline score. Secondary endpoints include significant improvements in pre- to post- treatment score on psychological indices (e.g., anxiety) and disease-specific quality of life. We will apply a similar approach using mixed effects regression analyses for these outcomes. Analyses will be performed using SAS 9.4 (SAS Institute, Cary, NC).

IX. Literature Cited

6. [name] OS. Hypnosis treatment of gastrointestinal disorders: A comprehensive review of the empirical evidence. *Am J Clin Hypn*. 2015;58(2):134-158.

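### Aim 2 promises baseline-adjusted treatment effects in a one-arm study; if baseline is a covariate, the model does not validly test the week-0 to week-12 change

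*Combined protocol and SAP*

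**What the plan says.** - **Design.** Section V.a: "This is a non-randomized observational study designed to provide preliminary data". Section VI.b: "Randomization procedures (if applicable): N/A". There is one group and no comparator.
- **Aim 2 endpoint.** Section III: "The primary endpoint for Aim 2 is significant reduction in pre- to post- treatment FD symptom scores". Section V.c places measurement of the primary endpoint at the end of treatment, and section VI.d makes that week 12.
- **Visits.** Section VI.d: "At baseline (week 0), week 6 (mid-treatment), week 12 (post-treatment), and at 12 weeks following end of treatment". That gives weeks 0, 6, 12 and 24.
- **Model.** Section VIII, Aim 2, specifies linear mixed effects regression, fitted separately for each primary outcome, and states: "These models will estimate treatment effects at each follow-up time point controlling for baseline score". It does not list the fixed effects, say whether week 0 is a response or a covariate, name a contrast or null hypothesis, or give an alpha. The only alpha in the document, 0.05, belongs to the Aim 1 tests.
- **Outcomes.** Section VIII names the DSSI and the NDI-SF as primary outcome variables. The symptom scale listed in section VI.d is a different one: "The PAGI-SYM measures 20 dyspeptic symptoms on a 6-point Likert scale". The DSSI is not in that list. The NDI-SF measures disease-specific quality of life, but section V.d says: "Secondary endpoints will be disease-specific quality of life, psychological indices, and patient satisfaction".

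**The concern.** Estimating an effect at each follow-up visit while adjusting for baseline is standard wording for a randomised comparison. There, the baseline covariate sharpens the difference between arms. Here there is no treatment variable; the only quantity available is change over time, and baseline is one end of that change.

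If baseline goes in as a covariate and the raw score is the response, the visit terms compare weeks 6, 12 and 24 with each other. None of them is the change from week 0. An analyst who then rebuilds the change by regressing change scores on centred baseline treats the sample baseline mean as a known constant. Its sampling error is left out of the standard error. Patients with a baseline score and no follow-up score also contribute nothing.

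Two analysts could follow section VIII faithfully and report different intervals and p-values for the primary Aim 2 result. On the covariate reading, a false claim of reduction is generally more likely than the nominal level. Calling the result a treatment effect also invites a causal reading. In one arm the change includes natural course and regression to the mean.

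**Working it through.** The plan gives no Aim 2 figure to reproduce, so the check derives the error of the covariate version directly.

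**Inputs.** From the documents: 23 enrolled and up to 20% drop-out (section V.c), so 23 × 0.8 = 18.4, taken as n = 18; visits at weeks 0, 6, 12 and 24 (section VI.d). Assumed, because the documents do not state them: no true mean change, bivariate normal scores, two-sided 5% level, baseline to week-12 correlation r of 0.3, 0.5 or 0.7, and k = week-12 SD / baseline SD of 0.8, 1.0 or 1.3.

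**Step 1: standard error.** Let D be week 12 minus week 0, with baseline SD s. Regressing D on centred baseline gives an intercept equal to the mean of D, which is the correct point estimate.

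- Variance the model reports: s²k²(1 − r²)/n
- True variance of the mean of D: s²(k² + 1 − 2rk)/n
- SE ratio = √[k²(1 − r²)/(k² + 1 − 2rk)]

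The true variance minus the reported variance is s²(1 − rk)²/n. The ratio therefore never exceeds 1, and equals 1 only when rk, the slope of the week-12 score on baseline, is exactly 1. Example with k = 1 and r = 0.5: √(0.75/1) = 0.866.

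**Step 2: type I error.** The residual variance is independent of the mean of D, so under no change

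Type I error = 2·P(t with n − 2 df > t(0.975, n − 2) × SE ratio).

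For n = 18, t(0.975, 16) = 2.120. In the example the effective cut-off is 2.120 × 0.866 = 1.836, giving 8.50%.

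| k | Quantity | r = 0.3 | r = 0.5 | r = 0.7 |
|---|---|---|---|---|
| 0.8 | SE ratio | 0.709 | 0.756 | 0.792 |
| 0.8 | Type I error | 15.25% | 12.86% | 11.25% |
| 1.0 | SE ratio | 0.806 | 0.866 | 0.922 |
| 1.0 | Type I error | 10.67% | 8.50% | 6.84% |
| 1.3 | SE ratio | 0.897 | 0.955 | 0.995 |
| 1.3 | Type I error | 7.53% | 6.00% | 5.10% |

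Results for n = 16 and n = 23 are each within 0.3 points of those for n = 18. With complete data, a mixed model with visit-specific baseline slopes and unstructured covariance gives this same week-12 test.

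**Step 3: simulation check.** With n = 18 and 200,000 runs per cell, the change-score version rejected 15.1/12.8/11.2%, 10.6/8.6/6.8% and 7.5/6.0/5.1% (rows k = 0.8, 1.0, 1.3). The paired t test rejected 4.9% to 5.1%.

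**Step 4: uncentred baseline.** If baseline is not centred, the intercept is the expected change at a baseline score of zero. With an assumed baseline mean of 3 SD, equal SDs, r from 0.3 to 0.9 and n from 16 to 23, its test rejected 12% to 85% of the time when the mean change was zero.

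**Step 5: week 0 in the response.** A REML model was fitted with four visits, unstructured covariance and Kenward-Roger degrees of freedom. It had 23 patients, 5 lost at random before week 12 (2 after week 0, 3 after week 6), correlation 0.7 among follow-ups and all follow-up SDs equal to k. Over the nine cells, with 10,000 runs each, the week-12 minus week-0 test rejected 4.7% to 5.3%, and all 90,000 fits converged. With complete data at n = 18 the degrees of freedom are 17, as in the paired t test.

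**Step 6: interval width.** Expected 95% CI width at n = 18, paired over change-score version: 1.41/1.32/1.26 (k = 0.8), 1.24/1.15/1.08 (k = 1.0), 1.11/1.04/1.00 (k = 1.3).

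**The case against.** The strongest reply is that section VIII never mentions a change score or a centred baseline. It refers to modelling trends over time, describes the secondary endpoints as pre-to-post improvements and plans a similar approach for them, which fits a model with week 0 in the response. On that reading, the baseline phrase is loose wording and the test is valid. This stands as far as it goes: the fault is conditional, and the percentages describe one way of carrying out the covariate reading. It does not remove the point, because the quoted sentence most naturally describes a covariate and nothing in the section settles the matter.

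Second, the size depends on assumptions. Values above 11% need a week-12 SD below the baseline SD. Entry criteria could narrow the baseline spread and push the ratio above 1, where the figures are 5.1% to 7.5%. With equal SDs and correlation 0.9 the error is only 5.5%. All of that is correct, and the effect may be one or two points.

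Third, this is a pilot sized for Aim 1, openly described as non-randomised, and the point estimate does not move with complete data. But section III makes a significant reduction the Aim 2 endpoint, and section V.c wants the data to power a later randomised trial, so the test and its interval matter.

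Fourth, patients with only a baseline score carry no direct information on change, and a paired fallback analysis drops them too. That makes the missing-data point minor. The DSSI and NDI-SF discrepancies are separate contradictions and are not evidence for this one; they are raised because the same sentences need editing.

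**Conclusion.** The concern holds. A one-arm study cannot estimate a treatment effect. The Aim 2 model, on its natural reading, either contains no term for the week-0 to week-12 change or gives that change a standard error that is too small unless the slope on baseline is exactly 1.

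For the change-score version, the error at a nominal 5% is about 7% to 11% with equal SDs, and about 5% to 15% over the whole grid. This rests on assumed SD ratios, correlations, normality and a two-sided 5% level. Confidence is medium, because the text could also be read as a model with week 0 in the response, for which there is no inflation. The interval, the p-value and the description of the result are at stake; with complete data the estimated mean change is not. The correction should be made, but it does not threaten the study.

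**What to change.** In section VIII, Aim 2, for each outcome:

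1. Put weeks 0, 6, 12 and the 3-month follow-up in the response, with visit as a categorical effect and a stated within-patient covariance. One example is unstructured with Kenward-Roger degrees of freedom, with the paired week-12 minus week-0 test as the fallback. Do not also enter baseline as a covariate.
2. Name week 12 minus week 0 in the FD symptom score as the one primary Aim 2 contrast, with a 95% CI and a stated alpha and sidedness.
3. Report it as mean within-patient change, not as a treatment effect.
4. In the same edit, reconcile the symptom instrument (DSSI in section VIII, PAGI-SYM in section VI.d) and the status of the NDI-SF (primary in section VIII, although quality of life is secondary in sections III, V.d and VIII itself).

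**Cost.** Only wording changes. The data, the software and the sample size, which was set on Aim 1, stay as they are. The interval will on average be 8% to 24% wider than the change-score version with equal SDs, and 0% to 41% wider over the grid, because that version is too narrow. The claim becomes more modest. An unstructured covariance has 10 parameters for 23 patients, which is why a fallback should be named. The fallback uses only patients with both week 0 and week 12.
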